Aim 1: Hypothesis 1a. Primary Analysis of the Study: We will assess if an EXS program in older sedentary PLWH enhances core NP domains (executive function, attention, and memory) compared to a SIS program. The change from baseline to 26 weeks after study intervention for each core domain Z- score and global Z-scores (comprised of the three core cognitive domain Z scores) will be compared between the EXS and SIS groups using t-tests. A 0.5 SD change in global Z-score is considered a clinically meaningful improvement and is currently being used for a pharmacotherapy (maraviroc) trial for HAND 149. In the present trial we anticipate that an EXS program will lead to >0.5 SD change in global Z-scores but we recognize that the precise threshold for individual perception of improvement is variable. For this analysis will use all random-ized subjects, under the intent-to-treat (ITT) paradigm. For participants missing a 26 week endpoint, a value will be imputed based on the lower (worse) half of the distribution from their arm (conservative approach).

Secondary analyses: Mean change in supplementary domain Z-scores at 26 weeks will be compared between the EXS and SIS groups for all randomized participants using the Z-test, under the following scenarios: (a) As treated (AT), with all subjects for whom the endpoint is available included in their allocated group; and (b) Per-protocol (PP), including only adherent participants ($\geq 80\%$ of study visits) for whom the 26 week endpoint is available. Additional multivariable secondary analyses will adjust for demographic and other relevant predictors, including plasma viral load and nadir CD4, gender,

depression, and other potential predictors that are significantly associated with the outcome at the 0.15 level using a backward model selection. In particular, the inclusion of gender and depression will allow for identification of differential changes in NP for men and women, and indirect effects of exercise mediated by depression 150-152. Since this is a medium-size randomized study we expect the unadjusted analysis to yield an unbiased estimate of the treatment effect. The outcomes will be collected only at baseline and follow-up, so a longitudinal analysis using generalized estimating equations or mixed effects models is not necessary as it would yield essentially identical results.

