Aim 2. Hypothesis 2a. Primary Analysis of the Study: We will assess if an EXS program improves brain structure and function more than a SIS program in older sedentary PLWH. Changes in brain volumetrics (hippo-campus, caudate, and anterior cingulate) and regional CBF (hippocampus, caudate, and anterior cingulate) at baseline and 26 weeks will be compared between EXS and SIS groups using a similar design as for Aim 1, including ITT, AT, and PS analyses. The brain imaging outcomes will be adjusted for the relevant markers of brain size. A Holm-Bonferroni correction will be used when evaluating the brain volumetrics across the different regions 154.

Secondary analyses: Similar analyses will also be performed for brain volumetrics and regional CBF in the amygdala, thalamus, and putamen. Additional analyses will control for relevant predictors, using a backward model selection strategy, as mentioned above.

Hypothesis 2b: We will assess if greater improvements in physical function due to EXS are associated with larger brain volumetrics and increases in regional CBF. We will test the mediating effect of improvement of physical function on neuroimaging measures in two ways: (i) between randomized groups, and (ii) within the EXS group. Linear models will be used to determine the mediating effect of the physical function markers (high/low physical activity and peak VO₂) on the change from baseline in structural and functional neuroimaging measures, by including these markers, together with group assignment, as predictors in the model. Within the EXS group similar linear models will be fit (without the group variable).

Hypothesis 2c. We will assess if greater improvements in cognition are associated with improved brain structure and function changes. Linear models will examine the relationship between neurocognitive performance (outcome) and brain structural and functional changes (predictors), using only the 100 participants randomized to the EXS group. These models will adjust for potential confounders, (e.g. plasma viral load and nadir CD4) that are significantly associated with the outcome at the 0.15 level using backward model selection.

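### Hypothesis 2c keeps a confounder only if it passes p<0.15 with the outcome in the same data, so real confounders can be dropped, leaving residual bias and intervals that are too narrow

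*Combined protocol and SAP*

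**What the plan says.** All references are to section F, Statistical Plan.

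- **Primary analysis, Aim 1 (Hypothesis 1a).** Changes in Z-scores "will be compared between the EXS and SIS groups using t-tests", without covariates.
- **Adjusted Aim 1 analyses.** These are secondary: "Additional multivariable secondary analyses will adjust for demographic and other relevant predictors, including plasma viral load and nadir CD4, gender", then depression, then "other potential predictors that are significantly associated with the outcome at the 0.15 level using a backward model selection". No closed list of candidates is given.
- **Aim 2, secondary analyses.** "Additional analyses will control for relevant predictors, using a backward model selection strategy, as mentioned above". The exploratory biomarker models and the logistic models for the secondary endpoints refer back to the same strategy.
- **Hypothesis 2c.** Linear models with cognition as outcome and imaging changes as predictors, "using only the 100 participants randomized to the EXS group". Potential confounders, with viral load and nadir CD4 only as examples, are adjusted for if they are "significantly associated with the outcome at the 0.15 level using backward model selection".

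For 2c the plan describes no confounder that stays in regardless, no separate sample for selection and no correction of the intervals for the selection step.

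**The concern.** A confounder biases the imaging coefficient in 2c because it is related to both imaging change and cognition. The plan's test looks only at the relation to cognition, and only at whether it reaches p<0.15 in this sample. A covariate with a modest effect on cognition but a clear correlation with imaging change can fail that test and still matter. Once it is removed, part of its effect moves to the imaging coefficient. The reported standard error also ignores that the model was chosen from the same data.

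2c is a numbered hypothesis under a primary aim. At stake is a brain-cognition association that looks better supported than it is.

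**Working it through.** **The plan's own figure.** Power ≈ Φ(d / √(1/n₁ + 1/n₂) − 1.96), two-sided 5% (the plan does not state alpha; this value reproduces its power).

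- 100:50, d = 0.49: 0.49/0.1732 = 2.83, power 80.8%
- 80:40, d = 0.55: 0.55/0.1936 = 2.84, power 81.1%
- 60:30, d = 0.635: 0.635/0.2236 = 2.84, power 81.1%

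Exact t gives 80.3%, 80.4% and 80.2%. The stated 80% is reproduced. These calculations concern unadjusted comparisons and do not involve the selection rule.

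**How often a real confounder is dropped.** Take an effect b on the outcome with residual SD 1. Its z-statistic centres near b√n, and the two-sided 0.15 threshold is 1.44. The sample is 100 EXS participants, or 80 at the plan's 20% drop-out.

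- n = 80, b = 0.20: 0.20 × √80 = 1.79; chance of being dropped ≈ Φ(1.44 − 1.79) = 36%
- n = 80, b = 0.15: 0.15 × √80 = 1.34; Φ(1.44 − 1.34) = 54%
- n = 100, b = 0.20: Φ(1.44 − 2.00) = 29%
- n = 100, b = 0.15: Φ(1.44 − 1.50) = 48%

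Correlation with the imaging measure raises these. Simulation at n = 80 gave 45% to 57%.

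**Type I error in 2c.** Simulation with the imaging term forced in, 8 candidates, backward elimination at 0.15, no true imaging effect and a nominal 5% test. Confounder effects are 0.15-0.20 SD; r is the correlation between confounder and imaging measure. Where a range is shown, it covers repeated runs or settings.

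| Assumed confounding | Backward selection | All kept |
|---|---|---|
| None | 6-7% | about 5% |
| r = 0.1-0.2, n = 80 | 5.8-7.3% | about 5% |
| r = 0.1-0.2, n = 100 | 5.2-7.8% | about 5% |
| One at r = 0.3 (effect 0.2 SD) | 7-8% | about 5% |
| Two at r = 0.3, n = 80 | 8.4-9.5% | about 5% |
| Two at r = 0.4, n = 80 | 14% | about 5% |
| Three at r = 0.4, n = 80 | 20.8-22.9% | about 5% |
| Three at r = 0.4, n = 100 | 20.1% | about 5% |

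**Bias and standard error.** Separate runs with 10 candidates and n = 100. With no adjustment the bias is (number of confounders) × r × effect.

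| Setting | Bias, unadjusted | Bias after selection | Mean SE / true SD |
|---|---|---|---|
| No confounders | 0 | 0.003 | 0.0994/0.1030 = 0.97 |
| Three, r = 0.3, effect 0.10 | 3 × 0.3 × 0.10 = 0.09 | 0.033 | 0.1050/0.1233 = 0.85 |
| Three, r = 0.4, effect 0.15 | 3 × 0.4 × 0.15 = 0.18 | 0.057 | 0.1142/0.1564 = 0.73 |

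In the last row the rejection rate was 41.8% unadjusted, 19.6% after selection and 4.8% with all covariates kept. Selection removes most of the confounding (0.057/0.18 leaves about a third), but the remaining bias comes with a standard error about 27% too small.

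**Adjusted treatment comparison.** Same procedure with the randomised arm forced in.

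| Candidates | n = 150 | n = 120 |
|---|---|---|
| 10, none predictive | 6.0% | 6.1% |
| 10, three predictive | 5.0% | 5.9% |
| 20, none predictive | 6.7% | 7.4% |

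The treatment estimate stayed unbiased. At n = 120 with non-predictive candidates, the mean standard error was too small by about 5% with 10 candidates (0.1909/0.2017) and 8% with 20 (0.1889/0.2063). Monte Carlo error is about ±0.7 points near 5% and ±1.3 points near 20%.

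**The case against.** **The size in 2c depends on assumptions.** This stands. Three uncorrelated confounders at r = 0.4 would explain 3 × 0.4² = 48% of the variance in 26-week imaging change; two would explain 32%, and two at r = 0.3 would explain 18%. Nothing in the documents supports such strengths, and below r = 0.3 the excess error is only 1 to 3 points. Viral load, one of the two examples named for 2c, should vary little because eligibility requires undetectable plasma HIV RNA. The top of the range is therefore a possibility and not a forecast.

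**Aim 1 may already force in the main covariates.** The selection clause can be read as applying only to the additional predictors, with viral load, nadir CD4, gender and depression fixed; the plan's later remark about including gender and depression favours that reading. This stands for Aim 1. The 2c wording does not allow it, because there the confounders themselves must pass the test.

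**Stronger readings.** A reader might infer that the rule compromises the trial's treatment effects. The documents do not support this. The primary test is an unadjusted t-test, and the plan keeps that estimate as its reference: "Since this is a medium-size randomized study we expect the unadjusted analysis to yield an unbiased estimate of the treatment effect". Randomisation keeps the adjusted estimate unbiased as well. A reader might also infer that every model uses the rule. The 1b and 2b models are specified as physical-function markers plus group (markers alone within EXS), with no selection stated. Brain-size adjustment is also planned without selection. Nor does the plan say that a selected model would be presented as fixed in advance; it is silent on that.

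**Conclusion.** The concern holds for Hypothesis 2c. Screening confounders on the outcome p-value in the analysed data can drop real ones, leaving residual bias and intervals that are too narrow. At nominal 5%, with n = 80-100 and 8 candidates, type I error is about 5.5-8% with no or weak confounding (r up to 0.2) and about 9-22% with two or three confounders at r = 0.3-0.4. It is about 5% when all are kept. The number of candidates, their strengths and their correlations are assumptions, because the plan leaves the list open; n = 80 further assumes completers only.

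For the secondary adjusted treatment comparisons the effect is minor: no bias, and type I error of about 5-6% with 10 candidates or 7-8% with 20. The figure of 20 is not in the plan. This is a cheap improvement to the plan and not a threat to the primary result.

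**What to change.** Before unblinding, replace backward selection in 2c with a short confounder set chosen on subject-matter grounds from baseline data already collected. An example is age, sex, education, nadir CD4, baseline depression and the baseline value of the outcome. Keep every term whatever its p-value. The list is illustrative: the investigators should choose variables plausibly related to both imaging change and cognition.

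Use a similar fixed list for the adjusted treatment models, and state there which terms are always included. If a selected model is also reported, label it exploratory or bootstrap the whole procedure, repeating the selection in each resample.

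The change is to plan wording; no new data are needed. The downside is a few degrees of freedom. If six such terms were all uninformative, the standard error in 2c would grow by roughly √(79/73) = 1.04, or 4%, at n = 80, and √(99/93) = 1.03, or 3%, at n = 100.

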2.8 This exploratory trial could guide professional recommendations. Recent treatment guidelines for PLWH suggest a role for physical activity as an adjunctive therapy to cART but specific recommendations are lacking⁸⁴. Currently, few older PLWH receive guidance from their healthcare providers concerning the potential benefits of a physically active lifestyle⁸⁵, especially in regards to brain health. This gap may reflect the relative absence of studies that have examined the effects of EXS on brain health in PLWH. This proposal uses a mixed model approach³⁰ that goes beyond typical observational and cross-sectional comparisons that have been previously used. Quantitative assessments of physical function (cardiorespiratory capacity and actigraphy) and brain function [NP and neuroimaging (volumetrics and CBF)] will be obtained in older sedentary PLWH at baseline and 26 weeks after an EXS or SIS program (2:1 randomization respectively). We will now capture aspects of the implementation process (e.g. program satisfaction, sustainability of behavior change) through interviews with staff and participants at several time points throughout the intervention. In addition, interviews will be conducted with participants to identify key barriers and facilitators for participation in an EXS program. This information, along with measures of modifiable participant engagement factors (e.g. stage of behavior change, self-efficacy, social support) will allow for scale-up to HIV clinics at multiple institutions.

C Study Objectives

C1 Primary Aims

Specific Aim 1. Examine the effects of exercise on cognitive function in older PLWH. Hypothesis 1a: A 26 week EXS program in older sedentary PLWH will enhance specific domain (executive function, attention, and memory) NP compared to a SIS program.

Hypothesis 1b: Greater improvements in physical function (daily physical activity and cardiorespiratory capacity) due to EXS will be associated with better cognitive performance.

Exploratory Hypothesis: Improvements in cognition due to EXS will be accompanied by reduced systemic inflammation and improved glucose regulation.

Specific Aim 2. Examine the effects of exercise on brain structural and functional measures in older PLWH.

Hypothesis 2a: A 26 week EXS program in older sedentary PLWH will improve brain neuroimaging measures (volumetrics and CBF) compared to a SIS program.

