Principal Stratification (PS) Analysis: An additional exploratory secondary analysis will be done using a Principal Stratification framework 153. This analysis compares the treatment arms separately for four subsets determined by whether participants would adhere to the study on any of the two study arms or not. Accordingly, the four sets are: adherers on both EXS, SIS; non-adherers on both EXS, SIS; adherers on EXS but not on SIS; adherers on SIS but not on EXS. In practice these data are available for only one of the two statuses that the subject is randomized to, but the second status is effectively imputed statistically. This innovative analysis will allow for separate evaluation of effects of EXS intervention for those who can and those who cannot adhere to the exercise plan, and will give insights into the differential effectiveness of the EXS program.

Hypothesis 1b: We will assess if greater improvements in physical function due to an EXS program are associated with better cognitive performance. We will test the mediating effect of improvements in physical function on cognitive performance in two ways: (i) between randomized groups, and (ii) within the EXS group. Linear models will be used to determine the mediating effect of the physical function markers (high/low physical activity and peak VO₂) on the change from baseline in core domain specific Z-scores and the global Z-score, by including these markers, together with group assignment, as predictors in the model. Within the EXS group similar linear models will be fit (without the group variable). Similar analyses for supplemental Z-score domains will be explored in secondary analyses.

Exploratory analyses: A similar analysis will be conducted, (i) including both groups, and (ii) within the EXS group, evaluating the mediating effects of changes in glucose regulation (fasting glucose and HOMA-IR) and chronic inflammation (hsCRP, D-dimer, IL-6) on cognitive endpoints. Other variables to be assessed include neurogenesis factors (BDNF, IGF-1, and VEGF). Additional analyses will control for relevant predictors, using a backward model selection strategy as described above.

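### Hypotheses 1b and 2b concern improvement in physical function, but the model sentence lists markers with no change term, time point or baseline value

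*Combined protocol and SAP*

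**What the plan says.** Section C1 states Hypothesis 1b as an association with improvement: "Greater improvements in physical function (daily physical activity and cardiorespiratory capacity) due to EXS will be associated with better cognitive performance". Hypothesis 2b has the same exposure, with brain volumetrics and CBF as outcomes.

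Section F (Statistical Plan) repeats this for 1b: "We will assess if greater improvements in physical function due to an EXS program are associated with better cognitive performance". It then names the target: "We will test the mediating effect of improvements in physical function on cognitive performance in two ways", between the randomised groups and within EXS. The paragraph on 2b likewise names improvement as the mediator.

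The next sentence defines the model. For 1b the linear models estimate "the mediating effect of the physical function markers (high/low physical activity and peak VO₂) on the change from baseline" in the cognitive Z-scores, "by including these markers, together with group assignment, as predictors in the model". For 2b the wording is "the mediating effect of the physical function markers (high/low physical activity and peak VO₂) on the change from baseline in structural and functional neuroimaging measures". The EXS-only models are the same without the group term.

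Other predictors in the same section are written as changes. The exploratory analyses are described as "evaluating the mediating effects of changes in glucose regulation (fasting glucose and HOMA-IR" and of inflammation markers, and Hypothesis 2c uses brain structural and functional changes as its predictors.

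**The concern.** In the model sentence, change from baseline belongs to the outcome only. High/low activity reads naturally as a level, and peak VO₂ has no time point. No cut-off defines high and low, and no baseline marker value is listed. An analyst working from that sentence could use a baseline level, a week-26 level, a split of either, or a change score.

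These choices test different things. A baseline level precedes the intervention and cannot carry its effect. A week-26 level mixes starting fitness with what the programme added. Without a baseline term, an association with either may only show that fitter people gain more on the tests, and a real link between fitness gain and brain gain can be diluted. An open choice can also be settled after results are seen. At stake is the trial's account of how exercise works, not its primary comparison.

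**Working it through.** **1. The plan's own figures.** No power is stated for 1b or 2b. The Aim 1 power statement covers the arm comparison, and alpha is not given. With two-sided 5% assumed, power = Φ(d/√(1/n₁+1/n₂) − 1.96):

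- 100+50, d = 0.49: 0.49/0.1732 = 2.829; power 0.81.
- 80+40, d = 0.55: 0.55/0.1936 = 2.840; power 0.81.
- 60+30, d = 0.635: 0.635/0.2236 = 2.840; power 0.81.

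The exact t gives 0.80 each time, so the stated 80% is reproduced. The two-sided 5% level and the expected completers (80 EXS + 40 SIS) are used below.

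**2. Assumptions not in the documents.** Baseline marker SD 1; SD of marker change s = 0.3, 0.5 or 0.7; baseline-change correlation ρ = 0 or −0.3; a correlation of 0.3 with outcome change, from marker change or from baseline as stated; EXS mean shift 0.5; median split for high/low.

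**3. How much a week-26 level reflects change.** With week 26 = baseline + change,

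corr(week 26, change) = (s² + ρs) / [s√(1 + s² + 2ρs)].

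- s = 0.5, ρ = 0: 0.25/(0.5 × 1.118) = 0.447. A true change correlation of 0.30 shrinks to 0.30 × 0.447 = 0.134. The week-26 level correlates 1/1.118 = 0.894 with baseline.
- s = 0.3, ρ = −0.3: the numerator is 0.09 − 0.09 = 0, so nothing remains of the link.
- s = 0.7, ρ = 0: 0.573, so 0.30 becomes 0.172.

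**4. Simulated rejection rates.** 2,000 trials per setting; ranges are over s. The two-arm model (80+40) includes group; EXS only has n = 80.

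- Case A: no link with marker change; baseline fitness correlates 0.3 with outcome change; ρ = 0. Rejections are false for the stated hypothesis.
- Case B: true change-change correlation 0.3; ρ = 0. Rejections are power.
- Case C: as B, with ρ = −0.3.

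| Marker entered | A two-arm | A EXS | B two-arm | B EXS | C two-arm | C EXS |
|---|---|---|---|---|---|---|
| Baseline level | 91-92% | 77-79% | 4-6% | 5% | 15-17% | 12-13% |
| Week-26 level | 77-89% | 60-74% | 16-47% | 13-34% | 6-24% | 4-18% |
| Week-26 high/low | 57-71% | 43-52% | 11-32% | 10-24% | 5-16% | 4-13% |
| Change | 4-5% | 5-6% | 92% | 78-79% | 91-92% | 78-80% |
| Change + baseline | 4-6% | 5-6% | 91-92% | 77-79% | 89% | 73-75% |

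**5. If change is what is meant.** Two weaknesses remain.

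- *Split.* In case B, dividing change into high and low lowers power from about 78% to 57% (EXS only) and from about 92% to 75% (two-arm).
- *No baseline term.* Suppose only baseline fitness drives the outcome (correlation 0.3) and ρ = −0.3. Change then acquires a spurious correlation of 0.3 × (−0.3) = −0.09. Roughly, 0.09 × √80 = 0.80 and 0.09 × √120 = 0.99, which give two-sided rejection of about 13% and 17%. Simulation gives 12-16%, against about 5-7% with baseline in the model.

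**6. Equivalence.** a·change + b·baseline = a·week26 + (b − a)·baseline. Once baseline is in the model, change and the week-26 value have the same coefficient and the same test.

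**The case against.** The strongest reply is that the plan already means change. In both hypotheses the sentence immediately before the model names improvement as the mediator, so the markers can be read as markers of that improvement. The exploratory work, written in terms of changes, is introduced as a similar analysis, which also supports that reading. This stands: the documents do not say that levels will be used. A reader might infer that the plan tests the wrong null, or that its mechanistic answer will be uninterpretable. The text does not support either, because both need the level reading to be settled.

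Nor is a level wrong in itself. By step 6, a week-26 value with baseline in the model is as good as change. The defect is the undefined marker and the missing baseline term.

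The percentages depend on outside assumptions. The documents give no SD of change and no correlations, and they name no week-26 level. Enrolling only sedentary people could narrow the baseline spread and reduce the contamination by starting fitness. The cut-off for high/low may also be defined in material not included here.

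These points limit the size of the problem without removing it. The target sentence and the model sentence still disagree. A cut-off defined elsewhere would not supply the time point, the change term or the baseline covariate. Step 5 also shows a cost under the charitable reading.

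**Conclusion.** The concern holds as an internal inconsistency with a better method readily available. The aim is improvement; the model lists markers without a change term, time point, cut-off or baseline value. If they are coded literally as levels without baseline, pre-existing fitness can produce rejection, and about half to nearly all of the power for a true change-change link is lost. If they are coded as change, the high/low split and the absent baseline term still cost power and error control.

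All simulated figures are conditional on the SDs, correlations, median split and two-sided 5% level listed above. They show direction and range and do not predict this trial's results. Hypotheses 1a and 2a and the stated power are untouched. The point should be corrected because 1b and 2b sit under the primary aims and currently have no determinate test.

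**What to change.** In Hypotheses 1b and 2b, for both the two-arm and the EXS-only models, replace the marker list with: change from baseline to 26 weeks in peak VO₂ and in actigraphy-measured daily physical activity, both continuous, each with its baseline value as a covariate. The week-26 value with baseline as a covariate is equivalent. Keep any high/low activity split as a supportive analysis with its cut-off and time point stated.

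The cost is one sentence per hypothesis and no new data, since sections E5 and E10 already schedule VO₂ testing and actigraphy at baseline and follow-up. In the simulated cases the baseline covariate costs at most about 5 points of power (80% to 75%, EXS only, ρ = −0.3).

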Exploratory analyses: A similar analysis will be conducted, (i) including both groups, and (ii) within the EXS group, evaluating the mediating effects of changes in glucose regulation (fasting glucose and HOMA-IR) and chronic inflammation (hsCRP, D-dimer, IL-6) on neuroimaging endpoints. Other variables that will also be assessed include neurogenesis factors (BDNF, IGF-1, and VEGF). Additional analyses will control

for relevant predictors, using a backward model selection strategy, as mentioned above.

Secondary endpoints: Scores from questionnaires that assess stage of behavior change, social support, self-efficacy, and exercise enjoyment will be incorporated with other quantitative outcome data. Logistic re-gression analyses will be conducted with response variables including: 1) successful complete (Y/N) 2) positive changes in cognitive function (Y/N); 3) positive change in brain structure and function (Y/N). The predictors will be the psychosocial or implementation factor scores. Odds ratios will be computed adjusting for demographic and other characteristics using backward model selection, as discussed before.

Additional Analyses: Baseline characteristics: Baseline demographic, medical, implementation factors, and lab characteristics of participants will be summarized by intervention arm (EXS or SIS) using N (%) for categorical variables, and mean, standard deviation, and range for numeric variables. Between-arms comparisons will use Fisher's exact test (FET) and Wilcoxon rank-sum test (WRST) for categorical and numeric variables, respectively. Neuroimaging comparisons will be adjusted via an analysis of covariance for measures of intra-cranial volume.

Study enrollment and drop-out: The number (%) of participants randomized, N (%) of participants completing 26 weeks, and N (%) of patients lost to follow-up will be summarized overall and by treatment arm, and compared between treatment arms using FET. For participants lost to follow-up we will record dates and reasons (if known) for loss to follow-up. Baseline demographic and medical characteristics will be compared between dropouts and completers using FET and WRST for categorical and numeric variables, respectively.

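### Hypotheses 1b and 2b promise a test of mediation, but the plan gives no EXS-versus-SIS model for marker change and no indirect effect, and it enters activity as high/low

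*Combined protocol and SAP*

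**What the plan says.** Section F, Hypothesis 1b, describes two analyses of mediation by physical function.

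- **Both arms.** A linear model of change in the core-domain and global Z-scores, "by including these markers, together with group assignment, as predictors in the model".
- **EXS arm only.** "Within the EXS group similar linear models will be fit (without the group variable").

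The coding of the markers appears in the phrase "the mediating effect of the physical function markers (high/low physical activity", followed by peak VO2. No cut-point is given, and it is unclear whether high/low also applies to VO2.

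Hypothesis 2b repeats the scheme for brain volumes and blood flow: "We will test the mediating effect of improvement of physical function on neuroimaging measures in two ways". The exploratory paragraphs of both aims reuse it for glucose regulation, inflammation and growth factors.

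Section F contains no EXS-versus-SIS model or test for change in activity or peak VO2. It has no definition of an indirect effect and no interval for one. It plans no comparison of the group coefficient with and without the markers. The between-arm comparisons under Additional Analyses cover baseline characteristics, drop-out, adherence, laboratory abnormalities and adverse events.

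The 1b and 2b paragraphs name no confounders. The nearest text is in the Aim 1 exploratory paragraph, "Additional analyses will control for relevant predictors, using a backward model selection strategy as described above", with a similar sentence for Aim 2. The rule it refers to keeps "other potential predictors that are significantly associated with the outcome at the 0.15 level using a backward model selection".

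**The concern.** Mediation by fitness has two parts: EXS must change fitness relative to SIS, and fitness change must relate to outcome change given arm. The stated two-arm model addresses the second part and supplies the direct effect. The first part is missing, and no result is named that would count as showing mediation. The Aim 1 secondary analyses reason in the same way: adding gender and depression as predictors "will allow for identification of differential changes in NP for men and women, and indirect effects of exercise mediated by depression".

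The EXS-only model has no treatment contrast, yet it is listed as one of the two ways to test mediation.

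Hypotheses 1b and 2b sit under the primary aims in section C1, and section B1, item 2.7, makes the relative strength of the mechanisms a focus of the project. At stake is a mechanistic claim that the analysis does not support. The high/low coding also works against the hypotheses, which concern how much function improves, whereas actigraphy yields a continuous measure before and after the programme.

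**Working it through.** **1. The plan's own figures.** The power paragraph gives 80% power at d = 0.49 (100 + 50), 0.55 (80 + 40) and 0.635 (60 + 30). With two-sided alpha 0.05 (assumed; none is stated), power ≈ Φ(d/√(1/n1 + 1/n2) − 1.96):

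- 0.49/0.1732 = 2.829, power 80.8%
- 0.55/0.1936 = 2.840, power 81.1%
- 0.635/0.2236 = 2.840, power 81.1%

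The figures reproduce. They concern the group comparison only; nothing is given for 1b or 2b.

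**2. Assumptions for the rest.** 80 EXS + 40 SIS completers (power paragraph), one normally distributed marker, and two-sided 0.05. The marker shift a (in SD), the marker-outcome correlation or slope b, and the median split are assumed. The percentages come from simulation; the formulas show where they arise.

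**3. EXS moves no marker (a = 0, true indirect effect 0).** The expected t for the marker term in the two-arm model is about r√117/√(1 − r²), with power ≈ Φ(t − 1.98). At r = 0.3: 0.3 × 10.82/0.954 = 3.40, and Φ(1.42) = 92%. Requiring the group-to-marker path as well multiplies this by about 0.05.

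| r | t | Marker term significant | Both paths: formula | Both paths: simulated |
|---|---|---|---|---|
| 0.2 | 2.21 | 59% | 0.05 × 0.59 = 3% | about 3% |
| 0.3 | 3.40 | 92% | 0.05 × 0.92 = 5% | about 5% |
| 0.4 | 4.72 | over 99% | 0.05 × 0.99 = 5% | 5-6% |

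**4. EXS does move the marker.** The standard error of a is √(1/80 + 1/40) = 0.194.

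- a = 0.8, b = 0.30: the a path has t = 0.8/0.194 = 4.13 and power 98%. The marker term alone is significant in about 91% of trials and both paths in 0.98 × 0.91 ≈ 90%.
- a = 0.5, b = 0.25: the a path has t = 2.58 and power 73%. The marker term alone is significant in about 78% and both paths in 0.73 × 0.78 = 57%.

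**5. High/low coding.** A median split of a normal variable keeps √(2/π) = 0.798 of its correlation. At b = 0.25 the effective correlation is about 0.20, t = 2.20 and power Φ(0.22) = 59%. Simulation, which also reflects the arms splitting unevenly, gives about 78% falling to 57%. At a = 0.8, b = 0.30 it gives 91% falling to 73%. Both pairs are for the marker term in the model the plan states.

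**6. Confounding.** Adding the marker model does not make marker change randomised. Take no true marker effect, a 0.5 SD shift, and a baseline factor correlated 0.2, 0.3, 0.4 or 0.5 with both marker and outcome. Both paths are then significant in 5%, 11%, 30% or 57% of trials unadjusted, and in about 4-5% with the factor prespecified as a covariate.

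**The case against.** **The hypotheses are worded as associations.** This is true in section C1 and in the opening sentences of 1b and 2b, and the stated models answer that question. However, section C1 attributes the improvement to EXS, and section F then promises mediation. The plan should either specify that test or drop the word.

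**The indirect effect can be recovered.** A reader might infer that these models give nothing beyond an association. That holds only for the EXS-only model. In one common sample, the group coefficient without the marker minus the coefficient with it equals the product of the two paths. But the plan does not say this will be done. Subtracting 1b from 1a need not give it either: 1a uses all randomised participants with imputed endpoints, while 1b states no analysis set.

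**The 59-99% is not this plan's error rate.** A reader might take it as one. The documents state no rule that a significant marker coefficient equals mediation, and section B1, item 2.6, reports that exercise improves cardiorespiratory capacity in this population. Zero shift is therefore a worst case, and step 4 shows how far the gap narrows.

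**The cost of high/low coding can be overstated.** Splitting the marker in both paths cuts joint-test power from 57% to 26%, or from 91% to 65%. The plan has no group-to-marker model in which to split it, so the step 5 figures are the relevant ones. They concern activity, unless VO2 is also split.

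**Confounders may be covered.** If the backward-selection sentence reaches 1b and 2b, false mediation in the step 6 scenarios is about 4%. It is 7% for a factor correlated 0.5 with the marker but 0.2 with the outcome. Its reach is not stated, so this is the smaller point.

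**Conclusion.** The concern holds as a gap in the specification of 1b and 2b. The plan names a mediation test, supplies half of it, and dichotomises a continuous marker without a cut-point. This is more than missing detail, because the one model given for both arms cannot by itself show that EXS acted through fitness.

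The practical size depends on how far EXS moves the marker. The gap between the two readings is 59-99% against 3-6% at no shift, 78% against 57% at 0.5 SD (slope 0.25), and 91% against 90% at 0.8 SD (slope 0.30). The high/low coding costs roughly 20 percentage points of power for the activity term. All of this rests on assumed path sizes, an assumed median split and 80 + 40 completers.

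A reader might infer that the trial's main conclusions are at risk. The documents do not support that: 1a and 2a are direct arm comparisons and do not use these models. The change should be made before analysis, for the sake of the mechanistic claims.

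**What to change.** 1. Enter activity and peak VO2 as continuous change from baseline.
2. In one common set of participants, fit marker change on group, and outcome change on group plus marker change. Adjust both models for baseline marker, baseline outcome and a short prespecified list of baseline confounders already collected (for example age, gender, education, depression score and nadir CD4).
3. Report the indirect effect with a percentile bootstrap 95% interval, base any mediation claim on that interval, and state the assumption of no unmeasured confounding.
4. Label the EXS-only models as associations and the mediation intervals as exploratory.

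The cost is SAP wording; no new data or visits are needed. The downside is fewer mediation claims, because both paths must now be supported.
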